Study protocol

NCT03232801

Title: A Mindfulness-Based Intervention for Older Women with Low Sexual Desire

Version date: August 1, 2022

Study Rationale

Sex is a fundamental component of overall well-being for many adults. Individuals who maintain a healthy sex life with aging live longer and have high quality of life. However, sexual function problems are common, particularly among midlife women; 39% of this population struggles with low sexual desire. This can affect not only a woman's sex life, but also negatively impact on psychosocial functioning and relationships.

Despite success in developing treatment for men, there has been a lack of treatment options for women. An increasingly accepted model of female sexual response emphasizes both physiologic and psychologic aspects of female sexual function. Pharmacologic treatments that only target physiologic response will only help a subset of women. In contrast, behavioral interventions have the potential to target both physiologic and psychological aspects of female sexual function. Using this rationale, this study will look at the use of a mindfulness study to improve sexual function in midlife women. Female sexual dysfunction is associated with sexually-related anxiety, autonomic nervous system imbalance, negative body image, discursive negative thoughts that distract during sex, and poor sleep.

Using this rationale, this study will look at the use of a mindfulness study to improve sexual function in midlife women. Mindfulness, a concept that emphasizes in-the-moment focus and non-judgmental bodily awareness, can target all these aspects of sexual dysfunction simultaneously by decreasing anxiety, improving autonomic imbalance, enhancing body image, reducing distracting thoughts, and improving sleep.

Treating sexual dysfunction will result in improvements in women's sexuality and can have the opportunity to go beyond sex to improve relationships and overall quality of life in aging adults. At least 85% of women in the intervention group will indicate somewhat or very satisfied on a measure of the intervention satisfaction.

A multi-component, mindfulness-based intervention, developed by [name] at the University of British Columbia, has shown preliminary efficacy in smaller studies for the treatment of desire, arousal, and sexual pain disorders (1-6). However, these studies lacked control groups or used wait-list controls. Additionally, this intervention was developed and tested primarily among women in their 30s and 40s. Whether and how this intervention works in older women is not known. Older women have unique physical and psychological sexual health needs that are not adequately addressed by the existing intervention. Older women are more likely to have medical conditions, such as hypertension (7,8) or diabetes (9), or to be using medications, such as antidepressants (10) or antihypertensives (11), that can affect sexual function. Women over 50 may also have musculoskeletal pain and orthopedic issues that can negatively impact sexual function. Additionally, older women are more likely to experience problems with vaginal dryness and dyspareunia than younger women, as these changes are most prevalent for women in their 50s, 60s and beyond (13-15, 18). Further, the sexual outcomes that are most important to older women differ from those of younger women; while younger women prioritize physical outcomes, older women may consider emotional outcomes more important (16-18). Cohort effects may influence the acceptability of the intervention between younger and older women, such as openness to mindfulness-based approaches (19). Finally, older women may have different social roles – such as caregiver – that may affect their relationship with their partners, sexual function, and overall wellbeing (20)(21). The adapted intervention should ensure that we address these unique sexual health needs of older women.

Known Risks and Benefits

Benefits

- Increased awareness of sexual genital sensations, attributed to increased awareness of present moment in their own bodies and decreased distraction
- May allow women to tap in to their physical arousal to enhance overall sexual arousal, desire, and satisfaction
- Decreasing anxiety, depression, and negative affect
- Improved body image
- Enhanced sleep quality

Risks

- Loss of confidentiality

- Injury during light yoga sessions

-

To minimize risk, participant information is kept on a password protected computer behind a firewall. Additionally, through Zoom, participants can participate and give as much information as they feel comfortable with. Additionally, all participants have the opportunity to change their name on Zoom and allow them to decide whether they would like to keep their camera on or not.

To reduce the risk of injury during yoga sessions, everyone is encouraged to only complete what they feel comfortable doing. Additionally, the yoga practice is kept as simple as possible and feasible for people of all ages and abilities.

Recruitment

Inclusion Criteria

In order to be eligible to participate in this study, an individual must meet all of the following criteria:

1. Provision of signed and dated informed consent form
2. Stated willingness to comply with all study procedures and lifestyle considerations/availability for the duration of the study
3. Females; Age 45 and older
4. Self-reported diagnosis of low sexual desire/decrease in sexual desire
5. Willingness to adhere to the 6-week program regimen

Exclusion Criteria

An individual who meets any of the following criteria will be excluded from participation in this study:

1. Does not have a sexual partner who they would like to be sexually active with
2. Requires assistance with bathing, dressing, toileting, and/or eating
3. Experiencing symptoms of depression
4. User of recreational drugs (excluding marijuana)
5. Consumes more than 7 alcoholic beverages in one week
6. Started a new medication for anxiety, depression, or other mental health problem in the past 3 months
7. Currently in a relationship with a romantic partner that has pushed or slapped them, or threatened them with violence
8. Very dissatisfied with their current romantic partner
9. Experienced high or very high levels of pain during or following vaginal penetration

Screen Failures

Screen failures are defined as participants who consent to participate in this study but are not subsequently assigned to the study intervention or entered in the study. Individuals who do not meet the criteria for participation in this trial (screen failure) because of meeting one or more exclusion criteria are thanked for their time and given the opportunity to ask any questions. Examples of exclusions are those that have severe pain with vaginal penetration, more than 7 drinks in a week, or those who do not have a partner with whom they would like to be sexually active.

Strategies for Recruitment and Retention

Each group (control and experimental) will have roughly 12-15 people in order to keep the group size comfortable. If participant number is fewer than 12 people per group, the sessions can still be held. As long as participants are willing to join and participate, the sessions can still go on. We are limiting our recruitment only to women who are 45 years and older. Due to the nature of this study, participants must be proficient in English.

Women will be recruited via: (a) flyers placed at local internal medicine, gynecology, and sex therapy clinics; (b) advertisements in University of Pittsburgh and UPMC staff e-mail newsletters, in newspapers, and on buses; (c) presentations to UPMC providers that care for midlife women; (d) social media advertisements such as Facebook; (e) the CTSI Research Participant Registry; and (f) Pitt + Me. The advertisement used for Facebook will only be posted on the personal pages of study staff, and we will not encourage others to "Share" the posting.

We will obtain verbal consent to perform telephone screening procedures, which involve minimal risk to the potential participant using the screening survey on RedCap. After telephone screening procedures, women who are eligible can be mailed or emailed detailed information on the study, if they are interested.

For participants, the study will initially be described over the phone. Participants will have the opportunity to ask questions about the study at this time. The Research Assistant will review the consent form and any risks associated with the study. Participants will be given the opportunity to verbally consent at that time or to read over more information that will be sent by email or snail mail. This will take about 20 minutes.

If uncomfortable with the study requirements, the participant may choose not to enroll in the study at this time. If the person decides to participate, they will be asked to complete a verbal consent over the phone. All documents specifically state that participation in the study is voluntary and the decision NOT to participate in the study will not have negative consequences for the participant.

In order to increase retention and keep participants interested, women will receive \$25 for completing each of the three assessments. An extra \$25 will be given for completing all three assessments, for a total of \$100 per participant. If interested, participants can complete an optional interview about the study at the completion of the sessions for a bonus of \$20.

STUDY INTERVENTION OR EXPERIMENTAL MANIPULATION DESCRIPTION

Women will be randomized into two separate groups. The active control group will attend six, two-hour sessions over six weeks in groups of approximately 12-15 women. The content of these sessions will focus on general health and aging (e.g., cardiovascular health, osteoporosis) and will include only limited information on sexual health. The use of an active control allows the study to control for group support and attention. It will also allow the study to explore women's willingness to be randomized.

Intervention will be given in the form of in person mindfulness training, including self-observation, meditation techniques, gentle yoga, and attention to breath. Additional content will include general sex education, sensate focus, and couples therapy, such as information on potential etiologies of sexual function and sexual response, bodily exploration exercises, and communication training.

Both women in the control group and the experimental group will be lead by the PI and a trained expert in mindfulness-based stress reduction. Women in both groups have the opportunity to complete an optional phone interview with a RA at the completion of the sessions on their experience.

Administration

Following the screening, participants will be sent a survey link to complete all the baseline activities. Once the intervention starts, participants will attend a weekly virtual session with other members of their group (control vs variable). These sessions will last for six weeks at approximately two hours each. In these sessions, they have the possibility of interacting with members of their group and with the leaders of each group. However, group participation is up to the participant; they are able to share as little or as much as they feel comfortable. Following the completion of the sessions, a survey will be sent to participant. These surveys will be identical to the baseline surveys, excluding the surveys on Demographics, Relationship Variables, Frequency of Sexual Activities, and Medical Variables. There will also be an Acceptability of Intervention survey sent out at the finish of the sessions. Participants will have one week to fill out and return the surveys, which will be tracked through RedCap.

At the 12 week mark, a final set of surveys will be sent out, identical to the baseline surveys, excluding the surveys on Demographics, Relationship Variables, Frequency of Sexual Activities, and Medical Variables. Participants will have one week to fill out and return the surveys, which will be tracked through RedCap.

Interventionist Training and Tracking

To ensure the completion of all surveys, in the week the survey is disseminated, progress will be monitored using RedCap. All surveys need to be returned within the week they are sent out so if progress is not being made by a participant, the RA will reach out up to three different times to send reminders and check in. The three contact points can be made via different methods, including through email and phone call.

Discontinuation/Withdrawal

An investigator may discontinue a participant from the study for the following reasons:

- Significant study intervention non-compliance, unless varying compliance is an aspect of the study objectives
- Lost-to-follow up
- Any event or medical condition or situation occurs such that continued collection of follow-up study data would not be in the best interest of the participant or might require an additional treatment that would confound the interpretation of the study
- The participant meets an exclusion criterion (either newly developed or not previously recognized) that precludes further study participation

Participants are allowed to withdraw at any time for any reason. Data up until the point a participant discontinued the study will be included in the study. Participants will not continue with surveys when participation is discontinued.

If a participant misses more than 2 meetings, they are withdrawn from the study. They are still eligible for payment if they completed the first survey. If there are further six-week sessions, a participant can move to a later session that may fit their schedule.

Loss to Follow-Up

The following actions must be taken if a participant fails to return their surveys in the correct amount of time:

- The site will attempt to contact the participant, remind them of the studies they have left to complete, counsel the participant on the importance of maintaining the assigned visit schedule, and ascertain if the participant wishes to and/or should continue in the study
- Before a participant is deemed lost to follow-up, the investigator or designee will make every effort to regain contact with the participant. The investigator or designee will make up to 3 different attempts at contact with the participant. These attempts will include reaching out via phone or email.
- Should the participant continue to be unreachable, they will be considered to have withdrawn from the study with a primary reason of lost to follow-up.

Weekly Meetings

Meetings for each group will be held on separate days. Following recruitment, a survey will be sent out to the participants to each group. Any survey system can be used to generate the surveys to gauge interest in the best day and time for the group (Qualtrics was used). Make sure that each group has a separate survey (i.e. an availability survey for both the mindfulness (experimental) and educational (control) group).

Give the groups around one week to answer, sending out 1-2 reminders. Once a day and time is decided on, meetings can begin. An email can be sent to participants with the upcoming dates and the Zoom link. To ensure participants remember the meeting, an email should be sent every week, 12-24 hours before the meeting with the zoom link.

Meetings are held every week for six weeks total. Meeting length is variable, but participants should prepare for a two-hour meeting.

At each meeting, a research assistant should take attendance and keep track of who is coming to the meetings. This is important to record to ensure participants are making it to at least 4 meetings.

Payment

Payment will be made through The University of Pittsburgh's Research Study payment system, Vincent. Information for payment includes Name, Address, and Birthdate. Participants are eligible to give their Social Security Number if they feel comfortable. If they would rather not include that information, 24% of their total will be taken. To help participants make the decision on whether to include their SSN or not, explain that it is needed for tax purposes. If a participant makes over \$600 in studies per year, it becomes taxable income. Following the completion of the Zoom sessions, an email will be sent out with information on payment and for the opportunity to schedule a quick phone call to go over all the information. As with loss to follow-up, three contact attempts will be made to participants. If they do not answer following the three attempts, they are not paid.

All Vincent cards are requested on the Vincent website. Each card in your inventory can be assigned to a participant. Some participants may have an existing account and card. If that is the case, have the participant

verify their account by asking for their birthdate or address. If they match, make sure to ask whether they would prefer to keep their old card or if they would like a new card.

After the completion of the twelve-week survey, cards are sent out or money is added to the existing card (in the case of a participant having a pre-existing account).

References

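### Treatment started after baseline is not recorded, and women discontinued because of it stop receiving surveys, so the exploratory 12-week FSFI and FSDS-R comparison is open to selective missing data and to co-treatment that cannot be described

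*Protocol*

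**What the plan says.** **Follow-up surveys (Protocol, Administration).** The survey at the end of the sessions is to be "identical to the baseline surveys, excluding the surveys on Demographics, Relationship Variables, Frequency of Sexual Activities, and Medical Variables". For the last round: "At the 12 week mark, a final set of surveys will be sent out, identical to the baseline surveys", with the same four modules left out. The only survey named as new after baseline is on acceptability: "There will also be an Acceptability of Intervention survey sent out at the finish of the sessions".

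**Why treatment matters (Protocol).** The Study Rationale observes that older women are more often found to be "using medications, such as antidepressants (10) or antihypertensives (11), that can affect sexual function". Discontinuation/Withdrawal lists, among the reasons for discontinuing a participant, a situation that "might require an additional treatment that would confound the interpretation of the study". The one medication-related exclusion is "Started a new medication for anxiety, depression, or other mental health problem in the past 3 months".

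**What discontinuation does (Protocol, Discontinuation/Withdrawal).** The list of reasons is permissive: the investigator may act on them. It also includes meeting an exclusion criterion that has arisen since enrolment. The text after the list keeps data collected up to discontinuation but ends surveys from that point.

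**SAP, Statistical analysis.** Satisfaction and likelihood of recommending the group at 7 weeks are primary. FSFI and FSDS-R at 12 weeks are exploratory and are analysed by linear regression of change from baseline. No rule is given for added treatment, missing outcomes or the analysis set.

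**The concern.** The Protocol treats medication and added treatment as able to alter the outcome or its interpretation, yet describes no means of learning about either after baseline. A woman who starts an antidepressant in week 3, for example, could fall under the exclusion-criterion route, but no follow-up item is described that would reveal it.

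Two things are at stake for the 12-week FSFI and FSDS-R contrast, the only comparison of sexual function and distress in the SAP. First, a woman discontinued before week 12 has no 12-week value. The decision is discretionary, and the principal investigator leads both groups (Protocol, Study Intervention section), so it is made with knowledge of the allocation. Loss of this kind need not be unrelated to outcome. Second, when the contrast is interpreted, nobody will be able to say how much outside treatment each arm received. Such treatment is plausible: recruitment includes "flyers placed at local internal medicine, gynecology, and sex therapy clinics", and the intervention's own content overlaps with sex and couples therapy.

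**Working it through.** The documents state no sample size calculation, effect size, SD, dropout rate or uptake figure, so there is no figure to reproduce. The check is a reading of the text, followed by an illustration on stated assumptions.

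**Step 1. What can happen to a woman who starts a new treatment after baseline.**

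- *Staff do not learn of it.* Administration leaves it to each woman how much she shares in sessions, and no survey item is described. She is analysed and nothing is recorded.
- *Staff learn of it and she stays.* The rule is permissive, so this is allowed. She is analysed, and the SAP has no rule for her.
- *Staff learn of it and she is discontinued before week 12.* Surveys stop. Change from baseline to 12 weeks cannot be computed, and a regression on observed changes omits her.

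**Step 2. Unrecorded or unhandled treatment (assumptions only).** Let g be the effect of the added treatment in SD units, and qT and qC its uptake in the intervention and control arms.

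Shift in the arm difference = g × (qT − qC).

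| qT | qC | g = 0.3 | g = 0.8 |
|---|---|---|---|
| 0.10 | 0.10 | 0 | 0 |
| 0.05 | 0.20 | −0.045 | −0.12 |
| 0.00 | 0.30 | −0.09 | −0.24 |
| 0.20 | 0.05 | +0.045 | +0.12 |

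The sign follows whichever arm has more uptake.

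To show the scale, take an assumed true effect d = 0.8 SD, two-sided 0.05 and the normal approximation: power = Φ(d/√(2/n) − 1.96). The n of 12 and 15 is the session size in Strategies for Recruitment and Retention, not a planned arm total.

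- n = 12: 0.8/√(2/12) = 1.96, power 0.50. With d = 0.8 − 0.24 = 0.56, power is 0.278. With d = 0.8 + 0.12 = 0.92, it is 0.615.
- n = 15: 0.8/√(2/15) = 2.19, power 0.591. With d = 0.56, power is 0.335. With d = 0.92, it is 0.712.

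**Step 3. Discontinuation (assumptions only).** Suppose a fraction q of one arm is lost, taken from the low end of a variable that has correlation ρ with the 12-week change. The mean of those remaining moves by ρ × φ(z_q)/(1 − q), where z_q is the normal quantile of q.

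- q = 0.10: φ(z_q)/(1 − q) = 0.195. The shift is 0 at ρ = 0, 0.06 at ρ = 0.3 and 0.12 at ρ = 0.6.
- q = 0.30: φ(z_q)/(1 − q) = 0.497. The shift is 0 at ρ = 0, 0.15 at ρ = 0.3 and 0.30 at ρ = 0.6.

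A simulation of 2,000,000 draws gave the same values. Loss from the high end reverses the sign, and the same loss in both arms cancels. In a group of 12 to 15, one woman is 1/15 to 1/12, or 7% to 8%; three are 20% to 25%.

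**The case against.** **The exposed outcomes are exploratory.** This stands. The primary outcome is a rating of the group itself at 7 weeks, and outside treatment has no evident route to it. It is touched only if a woman is discontinued before that survey.

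**If the aim is the effect regardless of later treatment, co-treatment is not bias.** This also stands, and it narrows the point. Under an all-randomised comparison, uptake is part of what is estimated. What remains is the loss of outcomes after discontinuation and the inability to describe uptake by arm. The SAP does not say which effect is intended.

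**The contents of Medical Variables are not listed.** True. It is an assumption that the module would have captured treatment for desire, so the remedy should not rely on it.

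**Collection may be over.** The SAP is written in the past tense. If so, only reporting can change.

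A reader might infer more than the documents support:

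- *That new treatment is always either unseen or removed.* The permissive wording leaves the middle course of Step 1.
- *That removal is uneven by arm.* No discontinuation figures are given. The same leaders run both groups, sharing is voluntary in both, both are offered the optional interview, and control sessions carry some sexual-health content. Unevenness is a risk, not a finding.
- *That the effect is diluted by 5% to 30%.* Those figures come from assuming control uptake 10 to 30 points higher and a benefit of 0.5 to 1.0 times the intervention effect (0.10 × 0.5 = 5%; 0.30 × 1.0 = 30%). The inputs exclude zero and the opposite sign. Sex education in the intervention arm could equally prompt care-seeking there.
- *That most women come from clinics offering such care.* Sex therapy and gynecology clinics are two settings within one of six recruitment channels.

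**Conclusion.** The point holds as a design weakness in the exploratory 12-week comparison. It is not a numerical error, and it is not a demonstrated bias. It rests on stated rules: a follow-up survey set without Medical Variables, two discretionary discontinuation routes, and a sentence that ends surveys once a woman is discontinued. The absence of any other treatment record is a reading of the two documents as published.

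Size and direction are unknown. In the illustration, the arm difference moves by anything from −0.24 to +0.12 SD through uptake, and one arm's mean by 0 to 0.30 SD in either direction through loss. Equal uptake, loss unrelated to outcome, or the same loss in both arms gives no shift. All of these depend on assumed uptake, effect and correlation. The case for acting is that the data to choose among them would not exist, while collecting them is cheap.

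**What to change.** 1. **Protocol, Administration.** Add a short item at baseline, 7 and 12 weeks, identical in both arms, on new or changed medication, treatment for desire or vaginal symptoms, sex or couples therapy, and outside mindfulness or yoga courses, with start dates.
2. **Protocol, Discontinuation/Withdrawal.** Amend the sentence that ends surveys, and both routes that lead to it (added treatment and an exclusion criterion arising during the study). Women discontinued for these reasons would still be sent the 7- and 12-week surveys, unless they withdraw consent or further data collection is not in their interest. This concerns data collection only and changes no woman's care.
3. **SAP.** Name the comparison of all randomised women as the main one for FSFI and FSDS-R, and state how missing 12-week values enter it. Tabulate new treatment and reasons for discontinuation by arm. Add one sensitivity analysis for women who started a treatment.

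The cost is a few REDCap items, one amended rule, one table and about 1-2 minutes of extra survey time per woman at each time point.

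If collection is complete, report discontinuations by arm and reason, and state as a limitation that treatment during follow-up was not recorded. Any later six-week cohorts, which the Protocol allows for, could still use items 1 and 2.

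### The protocol permits discontinuing a woman from the study for an exclusion criterion that arises after entry, and her surveys then stop, so outcome data can be lost for reasons related to outcome.

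*Protocol*

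**What the plan says.** The protocol's section on the intervention states: "Women will be randomized into two separate groups". Its Discontinuation/Withdrawal section opens a list with "An investigator may discontinue a participant from the study for the following reasons", and the last reason listed is "The participant meets an exclusion criterion (either newly developed or not previously recognized) that precludes further study participation". The same section goes on: "Data up until the point a participant discontinued the study will be included in the study". It then adds: "Participants will not continue with surveys when participation is discontinued".

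The Exclusion Criteria include "Experiencing symptoms of depression" and "Very dissatisfied with their current romantic partner". They also include high or very high pain with penetration, and having no partner with whom the woman wants sexual activity. Known Risks and Benefits lists, among the expected benefits, "Decreasing anxiety, depression, and negative affect". The Study Rationale expects gains in sexuality and relationships, and sets a target of at least 85% of the intervention group being somewhat or very satisfied.

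The SAP places the primary outcomes (satisfaction and likelihood of recommending the group) at 7 weeks, compared by chi-squared test. Change in FSFI and FSDS-R from baseline to 12 weeks is exploratory and is compared by linear regression. The SAP names no analysis population, no method for missing data and no sensitivity analysis.

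**The concern.** A criterion that is harmless at screening becomes a post-randomisation variable once it can end participation later. If the criterion is also something the intervention is meant to change, the women who lose their outcome data may differ systematically from those who stay. Neither analysis in the SAP has a feature that would correct for this.

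The wording leaves room for uneven use. The decision is discretionary. The principal investigator helps lead the sessions of both groups, so allocation is presumably known, and no masking of the discontinuation decision is described. The relationship and medical questionnaires are not repeated after baseline (Administration), so a new criterion would come to light only by chance. Partner and sexual topics are a main part of the intervention sessions and only a limited part of the control sessions, so such problems might surface more readily in one arm. That last step is an inference, not something the documents state.

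At stake are the between-group comparisons at 7 and 12 weeks and the satisfaction rate set against 85%.

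**Working it through.** **No stated figure to reproduce.** The documents give no total sample size, alpha, SD or expected loss. The first step is a reading; the rest is illustration under stated assumptions.

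**Step 1: what is lost, by time of removal.**

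| Removed | 7-week satisfaction | 12-week change in FSFI, FSDS-R |
|---|---|---|
| Before the 7-week survey | missing | missing |
| After the 7-week survey, before the 12-week survey | kept | missing |

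Keeping earlier data does not fill these cells. Satisfaction with the group has no baseline value, and a baseline score alone gives no 12-week change.

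**Step 2: shift in a mean difference (FSFI, FSDS-R).** Assume no true difference, normal outcomes, and removal from one arm only of the k women lowest on a trait correlated ρ with the outcome. With E₁ and E₂ the expected lowest and second-lowest of n standard normal values,

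shift in SD = ρ × (sum of |E| over the k removed) / (n − k).

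The value 13 lies within the 12 to 15 that the protocol gives for a session group. The value 30 is an assumed larger arm, because the protocol foresees further six-week series.

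- n = 13: |E₁| = 1.668 and |E₂| = 1.164. With ρ = 1, k = 1 gives 1.668/12 = 0.14, and k = 2 gives 2.832/11 = 0.26. With ρ = 0.5: 0.07 and 0.13. With ρ = 0.3: 0.04 and 0.08.
- n = 30: |E₁| = 2.043 and |E₂| = 1.616. With ρ = 1, k = 1 gives 2.043/29 = 0.07, and k = 2 gives 3.659/28 = 0.13. With ρ = 0.3: 0.02 and 0.04.

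Simulated false-positive rates for a two-sample t test at 5% run from about 5.1% (ρ = 0.3, k = 1) to 11.1% (ρ = 1, k = 2) at 13 per arm. At 30 per arm they run from about 5.1% to 9.0%. At ρ = 0.5 they are about 5.4% and 6.2% at 13 per arm (k = 1 and 2), and about 5.5% and 5.8% at 30. Equal and equally selective removal in both arms gives no mean shift.

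This covers a continuous outcome only. It does not evaluate the chi-squared test of the primary outcomes.

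**Step 3: the 85% target.** Observed rate = satisfied / (n − removed). With n = 15 and 3 dissatisfied women, 12/15 = 80.0% misses the target. If one of the three is discontinued before week 7, 12/14 = 85.7% meets it.

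Now suppose that true satisfaction is 75% and that one dissatisfied woman, if there is any, is removed. The exact binomial chance of reaching 85% changes as follows:

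| n | Everyone kept | One dissatisfied woman removed |
|---|---|---|
| 12 | 15.8% | 39.1% |
| 13 | 12.7% | 33.3% |
| 15 | 23.6% | 46.1% |

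The target concerns one arm, so equal removal in the control group does not offset this.

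**The case against.** The strongest reply is that this is permissive wording and not a procedure. The investigator may act, only where the criterion rules out further participation, and no re-screening is described. That stands. A reader might infer that eligibility is systematically re-checked after randomisation; the text does not say so.

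A reader might also infer that women who did badly were in fact deleted and that the results are biased. The documents report no such removal and give no basis for its direction, so that reading is not supported either.

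Three further points stand in part.

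- Depression, pain and partner dissatisfaction are not the same thing as dissatisfaction with a group programme. The link to the primary outcome is therefore weaker than the link to FSFI and FSDS-R, which are exploratory. Step 3 assumes that the woman removed was dissatisfied with the intervention.
- The upper end of Step 2 assumes that exactly the worst outcomes are removed, and from one arm only. At moderate correlation the false-positive rate rises by roughly 1 percentage point or less.
- A woman discontinued after returning the 7-week survey keeps her primary outcome.

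The rule for missing more than two meetings leads to the same halt in surveys, so the two points share a remedy. They are still distinct, because a woman with full attendance can be removed under this bullet.

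**Conclusion.** The point holds as a statement of what the text allows. A discretionary rule, tied to criteria related to the intervention's targets, ends outcome collection after randomisation, and the SAP contains nothing to offset the loss. It does not establish that bias occurred.

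Under one-arm removal of one or two women, with correlation 0.3 to 1, the mean difference moves by about 0.04 to 0.26 SD at 13 per arm and 0.02 to 0.13 SD at 30 per arm. It does not move if removal is equal in both arms. The firmer exposure is the 85% target, where a single removal can turn a miss into a pass, provided that the woman removed was dissatisfied. Arm size, removal counts and correlations are all assumptions. The reading of the text is secure; the size is not.

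**What to change.** For this bullet, separate stopping the sessions from stopping data collection. State that:

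- the existing 7-week and 12-week surveys are still sent, unless the woman withdraws consent for data collection or the section's separate bullet applies, on continued data collection not being in her best interest;
- she is analysed in her randomised arm;
- discontinuations are reported by arm and by criterion.

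The same edit to the sentence that ends surveys can also cover the missed-meetings rule. No view is taken on who should stop attending sessions.

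The SAP is written in the past tense, so follow-up may already be complete. In that case, report the counts by arm and criterion, and add a sensitivity analysis of satisfaction with all randomised women in the denominator, for example counting those without a response as not satisfied.

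The cost is small: a few sentences in each document, and two existing REDCap surveys sent to a few more women, with no new measures or staff. If data collection is over, the cost is one table and one extra analysis.
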